6.1 Handling of Missing and Incomplete Data

The following imputation of missing values will be done:

- PK measurements (urine or plasma) below the quantification limits will be considered equal to zero for all analyses.
- Missing PK data (e.g., skipped plasma sample collected or uncollected urine voids) will not be imputed.

7. General Statistical Considerations

All data will be presented in data listings. Data from subjects excluded from an analysis population will be presented in the data listings, but not included in the calculation of summary statistics.

7.1 Subject Disposition

The number of subjects who enroll in the study and the number and percentage of subjects who complete each assessment will be presented. The frequency and percentage of subjects who withdraw or discontinue from the study and the reason for withdrawal or discontinuation will be summarized.

7.2 Demographic and Baseline Characteristics

Continuous demographic and baseline characteristic variables (age, height, weight, and body mass index) will be summarized overall and by treatment using descriptive statistics (number of subjects, mean, standard deviation [SD], median, minimum, and maximum). The number and percentage of subjects in each class of categorical demographic and baseline characteristic variables will also be summarized.

7.3 Pharmacokinetic Analyses

7.3.1 Urine Pharmacokinetics

The primary endpoint is a comparison of 24-h urinary NDMA excretion for ranitidine versus placebo when administered with either low nitrite/NDMA meals (comparison between treatments A and B, respectively) or high nitrite/NDMA meals (comparison between treatments C and D, respectively). No adjustment for multiplicity is planned as these comparisons are considered two separate studies for purposes of our overall design. As an exploratory analysis, 24-h urinary DMA for ranitidine versus placebo will likewise be compared between treatments A and B (low nitrite/NDMA meals) and treatments C and D (high nitrite/NDMA meals). 24-hr urinary excretion of ranitidine (exploratory) will be calculated for treatments A and C, though no

comparisons are planned. Finally, as an exploratory measure, the two placebo-treated treatments (treatment D versus B) will be compared to determine if meals comprised of foods traditionally identified as being higher in nitrites/NDMA result in a higher 24-hr urinary excretion of NDMA or DMA compared to meals identified as being lower in nitrites/NDMA.

The cumulative amount of NDMA (primary), DMA (exploratory), and ranitidine (exploratory) excreted in urine over 24-h for placebo and ranitidine administration will be calculated for each subject. All urine voids over a 24-h period will be collected. Each separate void will be weighed in a tarred container. The volume of the void will be determined assuming a specific gravity of 1.01. Concentration of each collected sample will be used to determine a cumulative amount excreted as follows:

$$Ae_{0-24, \text{compound}} = \sum_{\text{time}} \text{Urine}_{\text{weight, time}} * 1.01 * \text{Conc}_{\text{urine, time}}$$

Cumulative amounts of DMA and ranitidine will be log-transformed. A mixed-effect analysis of variance (ANOVA) approach will be used for comparing arithmetic means (for NDMA) and geometric means (for DMA and ranitidine) looking at the effects of treatment, period, and sequence. For NDMA, testing will be one-sided at a 0.05 significance level, and a significant increase will be concluded if the lower bound of the one-sided 95% interval for the arithmetic mean difference excludes 0. For DMA and ranitidine, testing will be one-sided at a 0.05 significance level, and a significant increase will be concluded if the lower bound of the one-sided 95% interval for the geometric mean ratio excludes 1. The results will be transformed back to the original scale by exponentiation to provide treatment geometric means.

Normality assumption of the ANOVA will be verified using the Shapiro-Wilke test for normality and homogeneity of variances will be verified using Levene's test. If either assumption is not valid, a Wilcoxon signed-rank test will be used for the comparison rather than an ANOVA.

Individual and mean time course plots of NDMA, DMA, and ranitidine excreted over 24-hr will be evaluated for each treatment. All urine PK parameters will be summarized using descriptive statistics (number of subjects, mean, SD, coefficient of variation [CV], median, minimum, and maximum) for NDMA, DMA, and ranitidine. Individual time course plots will use actual sampling times. Treatment mean plots will use planned sampling times.

All calculations and the hypothesis testing will be done using R software.

Total fraction of the ranitidine dose excreted in urine ($Fe_{0-24, \text{ranitidine}}$) will be determined for Treatments A and C based on the cumulative amount of ranitidine excreted in urine over 24-h ($Ae_{0-24, \text{ranitidine}}$) divided by 300 mg. This will be calculated for each individual, summarized using descriptive statistics (number of subjects, mean, SD, CV, median, minimum, and maximum), and visualized graphically using box-and-whisker plots.

Renal clearance of ranitidine will be determined (only for Treatments A and C) by calculating the rate of excretion as the difference between the later and earlier compound level divided by the difference in times points (i.e., $[\text{amount}_{t_2} - \text{amount}_{t_1}] / [t_2 - t_1]$). The log-transform of the renal

excretion will be plotted against the midpoint of each time stop. This will be fit to a linear regression using least-squares fitting and the slope and intercept will be used to determine the overall renal clearance. This will be calculated for each individual and summarized using descriptive statistics (number of subjects, mean, SD, CI, median, minimum, and maximum). All calculations will be done using R software.

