FDA has also conducted tests that simulate the potential formation of NDMA from ranitidine after it has been exposed to acid in the stomach with a normal diet. Results of these tests indicate that NDMA is not formed in typical stomach conditions. Similarly, if ranitidine is exposed to a simulated small intestinal fluid, NDMA is not formed. Other in vitro experiments suggest a combination of nitrites, such as found in processed meats, and an acidic environment potentiate formation of NDMA. For that reason, prior to requesting removal of ranitidine products from the market, the FDA had advised consumers who wished to continue taking these medications to consider limiting consumption of nitrite-containing foods.

Separately, a previous study (Zeng and Mitch, 2016) in 10 healthy volunteers showed that single dose administration of ranitidine 150 mg was associated with ~400-fold increase in urinary NDMA excreted over 24 h. This level of increase is substantially greater than would be expected from laboratory testing. Further evaluation is necessary to determine if and how much NDMA is

produced from ranitidine in the human body and whether nitrite-containing foods may potentiate formation of NDMA in vivo.

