### 4. Investigational Plan

#### 4.1. Study Design

This is a randomized, placebo-controlled, single-dose, 4-period crossover study in 18 healthy subjects. Healthy subjects will be randomized to one of 4 treatment sequences (i.e., ABCD, ABDC, BACD, or BADC). Four treatments shown in Table 4-1 will be given to each subject over the four study periods (see Table 4-2). All subjects will be provided low nitrite/NDMA meals for the first two periods of the study and high nitrite/NDMA meals for the last two periods of the study. This ordering of meals is proposed to allow purchasing a single lot of perishable items for different meals and to simplify meal preparation and serving at the study site. These sources of variability are expected to exceed variability from sequence effects. Furthermore, the proposed randomization sequences only impact the exploratory objective comparing NDMA and DMA exposure resulting from different meals.

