### **4.9.6 Pharmacokinetic Analysis**

#### **4.9.6.1 Urine Pharmacokinetics**

Cumulative amount of NDMA (primary), DMA (exploratory), and ranitidine (exploratory) excreted in urine over 24-h for placebo and ranitidine administration will be calculated for each

subject. All urine over a 24-h period will be collected. Each separate void will be weighed in a tarred container. The volume of the void will be determined assuming a specific gravity of 1.01. Concentration of each collected sample will be used to determine a cumulative amount excreted as follows:

$$Ae_{0-24} = \sum^{\text{time}} \text{Urine}_{\text{weight,time}} * 1.01 * \text{Conc}_{\text{urine,time}}$$

For both NDMA (primary), DMA (exploratory) and ranitidine (exploratory) measures will be log-transformed and utilize a mixed-effect analysis of variance (ANOVA) approach for comparing geometric means with terms for treatment, period, and sequence as fixed effects. The results will be transformed back to the original scale by exponentiation to provide treatment geometric means. Testing will be one-sided and a significant increase will be concluded if the lower bound of the one-sided 95% interval for the geometric mean ratio excludes 1.

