3.1 Study Design

This is a randomized, placebo-controlled, single-dose, 4-period crossover study with 18 healthy subjects. Subjects will receive 4 treatments over the 4 study periods (see Table 1). Each subject will be randomized to 1 of 4 treatment sequences (i.e., ABCD, ABDC, BACD, or BADC). The treatment will consist of oral administration of either a single dose of ranitidine (300 mg) or placebo administered at time zero on each of 4 different treatment days. All subjects will be provided low nitrite/NDMA meals for the first 2 periods of the study and high nitrite/NDMA meals for the last two periods of the study. Subjects will check in on Day -2 for baseline assessments and will complete each 2-day period over the next 8 days, followed by checkout (see Table 2).

Two different full day menus of low nitrite/NDMA and high nitrite/NDMA meals have been developed. Meals will be identical for treatment periods 1 and 2 (low nitrite/NDMA meals) of the study and a separate set of identical low nitrite/NDMA meals will be served on the washout days prior to treatment. Likewise, meals will be identical for treatment periods 3 and 4 (high nitrite/NDMA meals) and a separate set of identical high nitrite/NDMA meals will be served on the washout days prior to treatment days. The last meal on Day -1, Day 2, Day 4, and Day 6 should be administered at approximately 6 PM to permit at least 12-hour fasting prior to dosing. Subjects will be provided with distilled water to drink throughout the study.

On study treatment days, the first meal will be provided at the time of dosing. Subjects will be instructed to swallow the medication with approximately 250 mL of room temperature distilled water and begin eating within two minutes after dosing. Subjects are required to eat each meal in its entirety during the study. If the meal is not finished, the reason should be recorded, along with what was not eaten, and a picture of the remaining food should be taken.

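### The planned meal comparison (D versus B) cannot be separated from study period, and the estimable drug-by-meal contrast is not planned

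*SAP*

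**What the plan says.** **Design.** SAP section 3.1: "Each subject will be randomized to 1 of 4 treatment sequences (i.e., ABCD, ABDC, BACD, or BADC"). Protocol section 4.1 fixes the meal order: "All subjects will be provided low nitrite/NDMA meals for the first two periods of the study and high nitrite/NDMA meals for the last two periods". The reasons given are food lots and meal logistics. The same section concedes that the restricted sequences affect the exploratory meal comparison, and only that.

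**Model.** SAP section 7.3.1 specifies a mixed-effect ANOVA "looking at the effects of treatment, period, and sequence". Protocol section 4.9.6.1 gives the same model "with terms for treatment, period, and sequence as fixed effects". If the normality or equal-variance check fails, the SAP switches to a Wilcoxon signed-rank test.

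**Comparisons.** SAP section 7.3.1 tests A against B and C against D without a multiplicity adjustment, because "these comparisons are considered two separate studies for purposes of our overall design". It adds an exploratory meal comparison: "the two placebo-treated treatments (treatment D versus B) will be compared to determine if meals comprised of foods" regarded as high in nitrite/NDMA lead to more urinary NDMA or DMA. Neither document plans a comparison of the ranitidine effect between the two meal types.

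**Question in the background.** Protocol section 1 lists, among the things needing evaluation, "whether nitrite-containing foods may potentiate formation of NDMA in vivo".

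**The concern.** There are two linked problems.

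First, no subject receives the low meal late or the high meal early. Any change over the study days, such as diet during confinement, carryover, assay batch or adaptation to the unit, falls entirely on the meal comparison. With the period term in the model, D-B has no unique estimate. Without it, D-B is the meal effect plus the period effect. The SAP nevertheless presents D-B as the comparison that settles whether the meals matter.

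Second, D-B contains no ranitidine, so it says nothing about whether nitrite-rich meals increase NDMA formation from ranitidine. That is a drug-by-meal interaction, (C-D)-(A-B). With only A-B and C-D tested separately, a reader interested in potentiation is left to compare two test results. A significant result with one meal and a non-significant result with the other is not evidence that the effects differ.

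**Working it through.** **1. The plan's own figure (ranitidine versus placebo).** SAP section 3.2 assumes a geometric mean ratio of 2, a CV of 100%, one-sided alpha 0.05 and 14 completers.
- Log SD = sqrt(ln(1 + 1²)) = 0.8326, taken as the SD of the paired log difference; delta = ln 2 = 0.6931.
- Noncentrality = 0.6931 / (0.8326/sqrt(14)) = 3.115 on 13 degrees of freedom, giving power of 90.4%.
- With 20% dropout, 14/0.8 = 17.5, so 18.

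The stated sample size reproduces. It concerns A-B or C-D, not the meal contrast.

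**2. Rank of the stated model.** Intercept (1), treatment (3), period (3) and sequence (3) give 10 columns. In every sequence the indicators satisfy C + D = period 3 + period 4. The rank is 9 for 16 subjects (4,4,4,4), 18 (5,5,4,4) and 14 (4,3,4,3). Adding subject columns does not remove the alias.

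**3. Which contrasts survive.** Write the expected response as treatment effect t plus period effect p. Add any constant k to tC and tD and subtract k from p3 and p4: every fitted mean is unchanged.

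| Contrast | Change under k | Estimable |
|---|---|---|
| A-B | 0 | yes |
| C-D | k - k = 0 | yes |
| (C-D)-(A-B) | 0 | yes |
| D-B | k | no |
| C-A | k | no |

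**4. Noise-free illustration.** Set all treatment effects to zero and assume a drift of 10 ng per period, so p = 0, 10, 20, 30. The documents give no drift.
- Drop treatment C or D: k = 0, so D-B = 0.
- Drop period 3: k = 20, so D-B = 20.
- Drop period 4: k = 30, so D-B = 30.
- A-B, C-D and (C-D)-(A-B) are 0 in each case.

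These fits describe the data equally well.

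**5. Without the period term.** With equal sequence sizes, D lies half in period 3 and half in period 4, and B half in period 1 and half in period 2. Raw D-B = (20 + 30)/2 - (0 + 10)/2 = 20 ng. With 18 subjects as 5,5,4,4 it is 25 - 100/18 = 19.4 ng. The whole amount is drift. In general, a linear drift of d per period gives a raw D-B of 2d: 10, 20 or 40 ng for d = 5, 10 or 20. SAP section 3.2 cites a placebo value of 110 ng from the earlier study; 20 ng is 18% of that (20/110).

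**6. Precision of the interaction.** With 4 subjects per sequence, the variance is 0.125σ² for A-B or C-D and 0.25σ² for (C-D)-(A-B). The standard error ratio is sqrt(0.25/0.125) = 1.41.

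On the log-scale assumptions of step 1, the interaction SD is 0.8326 × sqrt(2) = 1.177. One-sided 0.05 power for assumed ratios of ratios:

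| Ratio of ratios | 14 completers | 18 completers |
|---|---|---|
| 1.5 | 34% | 40% |
| 2 | 67% | 77% |
| 3 | 95% | 98% |
| 4 | 99% | 99.9% |

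A two-sided 0.05 test at a ratio of 2 has 53% power with 14 completers. These figures are illustrative, because SAP version 2.0 moved NDMA to the arithmetic scale.

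**The case against.** **The comparison is exploratory and the limitation is disclosed.** D-B is not primary, and protocol section 4.1 says the sequences affect the meal objective. Both statements are true. But that section does not say that meal is fully confounded with period, and its argument about sequence effects does not deal with period. The SAP carries no caveat.

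**Non-estimability may never arise in practice.** The ANOVA might be fitted separately by meal type, or the signed-rank fallback might apply. The fallback is plausible for NDMA: the SAP change log reports many values below the quantification limit, and section 6.1 sets them to zero. Separate fits, however, leave D-B with no model at all, since neither contains both treatments. The signed-rank test gives a result, but it has no period adjustment and is confounded as in step 5.

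**Potentiation is not a listed objective.** This stands. The protocol summary asks about ranitidine versus placebo under each meal, and A-B and C-D answer that. Potentiation appears in the background only, and neither document says the two results will be set against each other. The missing contrast is therefore an omission relative to the rationale and does not contradict an objective.

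**The interaction is not a clean answer either.** This also stands. It has low power for modest effects, and it remains confounded with any change in the drug effect between early and late periods. Additive and multiplicative potentiation can also disagree, so the scale must be stated.

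**Conclusion.** The concern holds. In the ANOVA as written, D-B is exactly aliased with periods 3-4 versus 1-2 at any sample size. Any number reported for it is either set by software coding or is meal plus period. The 0, 20 and 30 ng values demonstrate the alias under an assumed drift; they do not estimate the actual bias, which the documents give no means of sizing.

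The primary contrasts A-B and C-D are sound on this point. The interaction (C-D)-(A-B) is estimable from the same data, provided period effects are additive on the analysis scale and the drug effect is stable over the study days. The change should be made, but it concerns exploratory results and not the trial's main conclusion.

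**What to change.** In SAP section 7.3.1:

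1. Add (C-D)-(A-B) as an exploratory within-subject contrast for urinary NDMA and DMA, with a two-sided interval at a stated level. Use each analyte's planned scale: a difference of arithmetic mean differences for NDMA, and a ratio of geometric mean ratios for DMA. State the assumption of a drug effect that is stable over time, and that an interval including no effect is not evidence against potentiation.
2. Compute D-B as a simple paired difference outside the period model. Label it descriptive and confounded with study day, and remove the wording that it will settle whether the meals raise excretion.

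**Cost.** SAP text and a few lines of analysis code, with no new data or procedures. D-B loses its inferential claim, and the interaction is less precise than either drug contrast by a factor of about 1.41 in standard error. A clean meal effect would have required randomising meal order, which the design gave up for logistical reasons; no analysis can recover it.

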3.2 Sample Size

Eighteen healthy participants are planned for enrollment. It is estimated that a sample size of 14 completing subjects will provide at least 90% power at a 0.05 significance level to demonstrate an increase in 24-h urinary excretion of NDMA with ranitidine compared to placebo for a 1-sided log-transformed paired comparison. This assumes that geometric mean ratio between 24-h urinary NDMA with ranitidine and placebo is 2 and that the coefficient of variability is 100%. Enrolling 18 subjects allows for up to 20% dropouts.

Sample size calculations for the study are based on results from Zeng and Mitch (2016), which showed a 400-fold increase in NDMA for 150 mg ranitidine compared to placebo (47,600 ng versus 110 ng, respectively). The observed 24-h urinary excretion of NDMA with placebo for this and other studies ranged between 11-380 ng. It is not known if 24-h urinary excretion of NDMA with placebo is higher than what has been historically observed or if the fold-increase observed in Zeng and Mitch with ranitidine would be observed in a study controlling for meals with a randomized crossover design. The study sample size reflects assumptions that the overall fold-increase may be substantially lower but is still powered to detect an increase with assumptions as stated above.

4. Study Endpoints

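### The 24-h urinary excretion formula multiplies void weight by the specific gravity of 1.01 instead of dividing; coded as printed with per-volume concentrations, amounts come out 2.01% too high, with no effect on the tests

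*SAP*

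**What the plan says.** The primary endpoint is 24-h urinary NDMA excretion, and SAP 7.3.1 describes how it is calculated. The measured quantity is a weight: "Each separate void will be weighed in a tarred container". The next sentence gives the conversion: "The volume of the void will be determined assuming a specific gravity of 1.01". The formula that follows sums, over collection times, weight times 1.01 times concentration; its operative part in the SAP is "weight, time}} * 1.01". Protocol 4.9.6.1 has the same two sentences and the same multiplication, "1.01 * \text{Conc}_{\text{urine,time".

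The SAP 2.0 change log alters section 7.3.1 only by moving NDMA from geometric to arithmetic means, so the formula stands as current text. Neither document states the unit of the urine concentrations.

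Two later rules in SAP 7.3.1 use the amounts:

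- A significant NDMA increase is concluded if the "lower bound of the one-sided 95% interval for the arithmetic mean difference excludes 0".
- The ranitidine fraction excreted "will be determined for Treatments A and C based on the cumulative amount of ranitidine excreted in urine over 24-h", divided by 300 mg.

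**The concern.** Specific gravity is density relative to water. A void of known weight has volume equal to weight divided by specific gravity, so the printed formula does the opposite of the sentence it is meant to carry out. The same operator appears in both documents, so this is not a slip confined to one of them.

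This is the line a programmer would code for the primary endpoint and the line a second programmer would check against. Double programming from the SAP would reproduce the error rather than find it. The move to arithmetic means in SAP 2.0 also matters: on the ratio scale a common factor cancels, whereas a mean difference in ng carries it in full. What is at stake is the accuracy of the reported amounts and whatever is built on them, including the fraction excreted and any later modelling. The conclusion of the test is not at stake.

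**Working it through.** **Inputs.** Specific gravity 1.01, void weight as the measured quantity, and the printed factor × 1.01 (SAP 7.3.1, Protocol 4.9.6.1). Dose 300 mg (SAP 7.3.1). Historical placebo range 11 to 380 ng, with 110 ng on placebo and 47,600 ng on ranitidine in the cited earlier study (SAP 3.2). Assumptions: concentration is per unit volume, and water is taken as 1 g/mL.

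**1. Printed and intended conversion.** For a 100 g void:
- as printed: 100 × 1.01 = 101.0 mL
- from the specific gravity: 100 / 1.01 = 99.0 mL

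For a 24-h total of 1,500 g (illustrative) the two are 1,515.0 mL and 1,485.1 mL.

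**2. Size of the error.** Printed / correct = 1.01 / (1/1.01) = 1.01² = 1.0201, that is +2.01%.

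**3. If concentration were per gram of urine.** No factor would be needed, and the printed formula would be 1.01 / 1 = +1.00% too high. The sentence about volume would then have no purpose. The printed formula is wrong, and in the same direction, under both readings.

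**4. Effect in ng, at × 1.0201.**

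| Correct amount | As printed | Shift |
|---|---|---|
| 0 ng (period entirely below quantification) | 0 | 0 |
| 11 ng | 11.22 | +0.2 |
| 110 ng | 112.21 | +2.2 |
| 380 ng | 387.64 | +7.6 |
| 47,600 ng | 48,556.76 | +957 |

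These are historical values used for scale, not predictions for this trial.

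**5. Ranitidine outputs.** The fraction excreted is amount / 300 mg, so nothing cancels: an illustrative 0.300 would be reported as 0.306. Renal clearance is also built from excreted amounts. The log excretion rate rises by ln(1.0201) = 0.0199 at every time point, so the slope is unchanged and the intercept shifts.

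**6. Effect on the tests.** Let k = 1.0201 multiply every amount.
- NDMA, arithmetic scale: the estimated difference, its standard error and the lower bound are all multiplied by k. The t statistic is unchanged and the bound keeps its sign.
- DMA, log scale: ln k is added to every value and cancels in any treatment contrast, so the geometric mean ratio is unchanged. The back-transformed treatment means for DMA and ranitidine do carry the factor.
- Wilcoxon signed-rank: signs and ranks of the differences are unchanged.
- Shapiro-Wilk and Levene: unchanged by a common scale factor, or by a common shift on the log scale.
- Sample size: a common factor leaves the planned ratio of 2 and the 100% coefficient of variation as they were, so the power is unaffected.

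A numerical check on 18 simulated pairs, four placebo values set to zero, agrees. Before and after scaling, t = 2.646, one-sided p = 0.00849 and Wilcoxon p = 0.00329. The lower bound moves from 30.11 to 30.71, a ratio of 1.0201.

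**7. A possible partial offset.** Protocol 4.7.1.2 adds 240 µL of sodium hydroxide to 40 mL of urine in Aliquots A and B, but not C. That dilutes the concentration by 40 / 40.24 = 0.9940. If A or B is assayed and the laboratory does not correct for the dilution, the net error against the true amount is 1.0201 × 0.9940 = 1.0140, about +1.4%. On the per-gram reading it would be 1.01 × 0.9940 = 1.0040, about +0.4%. The documents do not say which aliquot serves which analyte or whether a correction is made.

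**The case against.** The contradiction itself is hard to dispute; the case on the other side is about size and certainty.

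The 2.01% depends on two things the documents do not settle: that the R code follows the printed line, and that concentration is per unit volume. That is fair, and both conditions belong with the figure. The second is strongly implied, since weight is converted to volume for use with the concentration, and the alternative still leaves +1.00%. The sodium hydroxide offset can be assigned to no particular analyte, so it is a caveat rather than an estimate.

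Materiality is low. The 1.01 is itself an assumed constant, the trial is planned around a 2-fold effect with 100% variability, and no decision can change. That also stands, and it is why the point is minor. It does not make the formula right: unlike assay noise, the error is systematic and does not average out over voids or subjects.

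A correction that limits the sum to post-dose voids might seem to add a separate change, because a 0 h pre-dose sample is also collected. That limit only spells out what excretion from 0 to 24 h means; the substantive correction is the division.

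**Conclusion.** The formula is wrong as written in both documents. With per-volume concentrations and code that follows the printed line, all 24-h amounts are overstated by 2.01%. The same holds for the NDMA mean differences (A versus B, C versus D and D versus B) with their bounds, and for the ranitidine fraction excreted. Ranitidine renal clearance is affected through the intercept. With per-gram concentrations the overstatement would be 1.00%. Amounts recorded as zero stay zero. No test result, geometric mean ratio, decision or power statement is affected, because the factor is positive and common to all treatments. The point is minor. Whether the program contains the error cannot be seen from the documents.

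**What to change.** In SAP 7.3.1 and Protocol 4.9.6.1, replace the formula with: Ae0-24 = sum, over post-dose voids up to 24 h, of (void weight / 1.01) × concentration. State the concentration unit next to it. Check that the R code divides, and rerun the derived amounts, fraction excreted and renal clearance if it does not. It would also help to record which aliquot is assayed for each analyte and whether the laboratory corrects for the added sodium hydroxide.

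The cost is one formula line in each document and a check of one line of code. Design, sample size, decision rules and study conduct are untouched.

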2.0	General (Rationale)	NDMA analyses will be based on arithmetic means instead of geometric means. Blinded review of the bioanalytical data revealed that a large number of urine and plasma samples for NDMA were below the lower limit of quantification (LLOQ). For multiple subjects, all samples from 1 or more study periods were below the LLOQ. As zero values cannot be log-transformed for geometric mean analyses, these periods would have been removed from analysis. Furthermore, as analyses are paired, these subjects would have been removed from analyses. Utilizing arithmetic mean will allow data from all subjects and all periods to be used in the planned analysis. Ranitidine and DMA analyses will remain the same (i.e. utilizing geometric means).
	7.3.1	Analysis of urine concentrations Analysis of NDMA urine 24-hr excretion will be performed using arithmetic means instead of geometric means.
	7.3.2	Plasma pharmacokinetics Descriptive statistics for plasma PK parameters of NDMA will be calculated using arithmetic means.

1. Introduction

This document outlines the proposed statistical methods for data analysis of data collected from Protocol ‘SCR-010 Clinical study to investigate the urinary excretion of N-nitrosodimethylamine (NDMA) after ranitidine administration’.

2. Objectives

The following analysis plan provides the framework for the summarization of the data from this study. The analysis plan may change due to unforeseen circumstances but will be finalized prior to database lock. Any changes made after the database lock will be documented and justified in the clinical study report.

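### SAP 7.3.1: the switch to a signed-rank test can remove the NDMA bound that defines a significant increase, and part of the trigger does not fit a paired comparison

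*SAP*

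**What the plan says.** SAP 7.3.1 has two primary comparisons of 24-h urinary NDMA, A with B (low meals) and C with D (high meals), and keeps them apart: "No adjustment for multiplicity is planned as these comparisons are considered two separate studies for purposes of our overall design". The analysis is a mixed-effect ANOVA with treatment, period and sequence. For NDMA it compares arithmetic means, one-sided at 0.05, and "a significant increase will be concluded if the lower bound of the one-sided 95% interval for the arithmetic mean difference excludes 0".

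The following paragraph adds the checks: "Normality assumption of the ANOVA will be verified using the Shapiro-Wilke test for normality and homogeneity of variances will be verified using" Levene's test. Then: "If either assumption is not valid, a Wilcoxon signed-rank test will be used for the comparison rather than an ANOVA". It names no analyte, so it covers NDMA. It does not give the level of the checks, the quantity tested (residuals, differences or raw totals), or whether they run per meal type or once in a four-period model. It also gives no separate criterion, estimate or rule for zero differences on the rank path. Mean, SD, CV, median and range are summarised whichever path is taken. Protocol 4.9.6.1 has no such fallback.

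Under SAP 6.1, values "below the quantification limits will be considered equal to zero for all analyses". The version 2.0 Change Log moved NDMA to arithmetic means because zeros cannot be logged: "For multiple subjects, all samples from 1 or more study periods were below the LLOQ". The aim was that "Utilizing arithmetic mean will allow data from all subjects and all periods to be used in the planned analysis". The log does not mention the switch.

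**The concern.** The criterion and the fallback do not fit together. A signed-rank test yields no arithmetic mean difference and no bound for one, and it has no period term. If a check fails, the stated criterion cannot be evaluated and the adjusted estimate of the NDMA increase is not part of the primary result. The Protocol background asks not only whether ranitidine produces NDMA in the body but how much, so the size of the difference (in ng, the unit used in SAP 3.2) matters.

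The trigger is also doubtful. If Levene's test compares the two arms within a meal type, it examines a property the paired comparison does not need. Under a multiplicative effect it fails mainly when ranitidine raises NDMA, so the bound tends to disappear when there is an effect to quantify.

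**Working it through.** **1. The plan's own figure.** SAP 3.2 states that 14 completers "will provide at least 90% power at a 0.05 significance level to demonstrate an increase in 24-h urinary excretion of NDMA", with geometric mean ratio 2 and CV 100%, using a one-sided log-scale paired test.
- SD of the paired log difference: √ln(1+1²) = √0.6931 = 0.8326.
- Noncentrality at n=14: (0.6931/0.8326) × √14 = 3.115. Noncentral t with 13 df gives power 0.904; n=13 gives 0.881. So N=14 is reproduced, and 14/0.8 = 17.5 rounds up to 18.
- If 100% were the CV of each measurement with independent periods, the SD would be √2 × 0.8326 and power at n=14 would be 0.670. The stated figure therefore fixes the SD of the difference at 0.833, but not the marginal SD and the correlation separately.

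**2. Models consistent with that figure.** The SD of the difference is σ√(2(1−ρ)). Three pairs give 0.83:
- σ=0.589, ρ=0: 0.589 × 1.414 = 0.833
- σ=0.833, ρ=0.5: 0.833 × 1 = 0.833
- σ=1.177, ρ=0.75: 1.177 × 0.707 = 0.832

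**3. Simulation inputs.** From the documents: n=14 and 18, ratio 2 (and 1), one-sided 0.05, unquantifiable values set to zero. Assumed: lognormal totals, placebo median 60 ng, totals zeroed below 0, 60 or 100 ng, both checks at 0.05, one period-adjusted model per meal type, Shapiro-Wilk on its within-subject residuals, and Levene's test (median-centred) on the two arms.

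**4. How often the switch happens at ratio 2.** With σ=0.833 and ρ=0.5:

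| n | zeroed below 0 ng | 60 ng | 100 ng |
|---|---|---|---|
| 14 | 39% | 31% | 51% |
| 18 | 57% | 44% | 62% |

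Across all three pairs in step 2 the range is about 18-74%. It also depends on what is tested. A separate run (placebo median 110 ng, σ=0.833, ρ=0 or 0.5, up to 80% of placebo totals zeroed, mean-centred Levene's test) applied Shapiro-Wilk to the paired differences and gave 50-88%. The SAP does not say which quantity is meant.

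**5. What it does to the decision.** The two-stage rule differs from ANOVA alone in about 0.5-17% of comparisons at ratio 2. With σ=0.833 and ρ=0.5, type I error is 3.6-6.2% for the two-stage rule and 3.2-5.6% for ANOVA alone, with simulation error of about 0.4 points. Two-stage power is usually equal or higher.

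**6. Levene's test.** A per-meal paired comparison uses n within-subject differences, with variance σ²_R + σ²_P − 2cov. Nothing requires σ_R = σ_P. Doubling every value doubles the SD and multiplies the variance by 4, so a real effect triggers the test. With σ=0.833 and ρ=0.5 it rejects in 13-43% at ratio 2, against about 1-4% at ratio 1.

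**7. Zero differences.** By default a signed-rank test drops subjects with zero in both periods of a meal type. With σ=0.833 and ρ=0.5, n=18 and ratio 2, the simulated average is 0 to 6.8 of 18, depending on the assumed pattern of zeros. The Change Log gives no count of such pairs.

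**The case against.** The strongest reply is that little is lost. The sentence setting NDMA testing at one-sided 0.05 carries no condition, so a signed-rank p-value below 0.05 is the plain reading on the rank path. Arm means and SDs are reported anyway. A signed-rank test can also be inverted to a Hodges-Lehmann shift with an interval in ng. All of this stands. A reader might infer that success becomes undefined or that no amount can be reported; the documents support neither. What is missing is narrower: the stated bound and the period-adjusted mean difference. The SAP does not plan a Hodges-Lehmann interval.

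A second reply is that the fallback protects against skewed data. That also stands, because it usually matches or improves on ANOVA power. A reader might infer that the ANOVA bound should become the only rule, but that is a trade-off and not a correction.

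Third, Levene's test is not always out of place. In one four-period model with a pooled variance, some check of homogeneity is relevant, and the SAP does not say which model is fitted. The criticism is limited to the two arms of a per-meal paired comparison.

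Fourth, the loss of zero-zero pairs is unquantified. A subject with only one all-zero period keeps a nonzero difference and stays in the rank test, so the version 2.0 aim is not defeated for those subjects.

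**Conclusion.** The point holds in limited form. SAP 7.3.1 defines a significant NDMA increase by a bound that its own next paragraph may leave uncalculated. The test decision survives through the one-sided 0.05 level; the bound and the adjusted mean difference do not. The switch is likely and not a remote contingency: about 18-74% of comparisons at ratio 2 under the models in step 2. The decision itself changes in about 0.5-17%.

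A reader might infer inflated false-positive risk from the two-stage rule. The simulations show no material inflation. The rates rest on assumed lognormal totals, assumed zero patterns, checks at 0.05 and a per-meal model, none of which the SAP states, so they show likelihood and do not forecast this trial. The textual gap does not depend on them. Severity is minor to moderate: this concerns the specification and reporting of the primary result, not its validity.

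**What to change.** Amend SAP 7.3.1 before database lock; SAP section 2 allows this, and later changes would need justification in the study report.

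1. For NDMA, for both A-B and C-D, always report the ANOVA arithmetic mean difference with its one-sided 95% lower bound (equivalently a two-sided 90% interval), whatever the checks show. Note that the normal-theory upper limit runs low with skewed data: with σ=0.833 and ρ=0.5 at ratio 2 it fell below the true difference in 10-16% of simulated trials instead of 5%.
2. Remove Levene's test on the two arms as a trigger for the paired comparison here, and for the paired t-test in SAP 7.3.2, which likewise uses only differences (7.3.2 was not simulated).
3. If the signed-rank path is kept, state its criterion (one-sided p<0.05), handle zero differences by Pratt's method, and give a Hodges-Lehmann shift with its interval in ng.

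The cost is wording and a few lines of output, with no new data. Which test should be the single decision rule is for the sponsor. Using the ANOVA bound alone costs about 0-16 points of power in these scenarios (88% to 74% in one of them), with a small gain in a few.
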